8.5 End of Treatment

The end of treatment (EOT) visit is done when the subject discontinues study treatment for any reason. The decision to discontinue study treatment due to progression must be based on the

evaluation of lab assessment. If the decision to permanently discontinue the study treatment is made during a scheduled visit, then the EOT visit should be performed instead of the scheduled visit. If the decision is made between scheduled visits, an EOT visit should be performed no later than 30 days after the last treatment administration or prior to the start of new subsequent anti-cancer therapy, whichever occurs first.

8.6 Follow-Up

Subjects who received ruxolitinib on study and discontinue therapy for reasons other than disease progression should continue to have standard of care disease assessments done until progression or start of subsequent therapy. At such time, follow-up or overall survival status will take place every three months +/- 7 days until death, lost to follow up, or until the criteria defined for the final analyses (Section 13.4.1) are reached. However, in the event the criteria for the final analysis are met, and there are subjects who have not yet been discontinued from study treatment, subjects in follow up will continue to be followed until all subjects have discontinued study treatment and completed the required 30 day safety monitoring period (Section 9.3). Follow-up beyond the safety monitoring period is only required for subjects who received ruxolitinib.

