 - Urine immunofixation electrophoresis (UIFE)
 - For subjects whose disease is not measurable by UPEP at Baseline, a 24-hour urine sample for UPEP and Urine immunofixation (UIFE) will be collected every 3 cycles at a minimum.
- If disease has not progressed and new anti-cancer treatment has not been started after study treatment discontinuation, response assessment samples should also be collected per standard of care during the follow-up visits.
- Radiologic imaging of plasmacytoma as clinically indicated (same technique to be used throughout the trial). Positron emission tomography/computed tomography (PET/CT) scan or magnetic resonance imaging (MRI) as clinically indicated
- Bone skeletal survey as clinically indicated and to confirm progression if needed.
- Phase II/Run-In only: Beginning with Cycle 1, disease evaluation results to assess response should be available for investigator review prior to dosing on Day 1 (up to 7 days prior) of each cycle until initiation of ruxolitinib. Cycle numbers start over with the initiation of ruxolitinib (the first cycle of ruxolitinib will be Cycle 1) and a new disease response baseline will be established (Phase II/Run-in subjects who cross over to Phase II/Ruxolitinib).

8.4.2 Laboratory assessments:

- Hematology - hemoglobin, WBC with differential, and platelet count
- Blood chemistries - sodium, chloride, potassium, magnesium, phosphate, uric acid, BUN, glucose (fasting at baseline), ALT/AST (SGPT/SGOT), alkaline phosphatase, total protein, total bilirubin, albumin, serum creatinine and estimated creatinine clearance, calcium and lactate dehydrogenase (LDH).
- Brain Natriuretic Peptide (BNP)
- Disease specific laboratory evaluations as noted above.
- Correlative studies (blood and bone marrow). Note: ruxolitinib must have been initiated in order to collect correlatives post-baseline.

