13.2.3 Progression-Free Survival and Time to Progression

PFS is defined as the duration of time from the initiation of study treatment with ruxolitinib to first occurrence of either progressive disease or death. Disease progression as described by IMWG Criteria (Appendix [18.3](#)). The date of progressive disease is the date of the initial assessment that identified progressive disease. If the subject dies without documented disease progression, the date of progression will be the date of death. For surviving subjects who do not

have documented disease progression, PFS will be censored at the date of last disease assessment. For subjects who receive subsequent anti-cancer therapy prior to documented disease progression, PFS will be censored at the date of last disease assessment prior to the commencement of subsequent therapy. Subjects who have an initial PFS event immediately following 2 or more consecutive missed assessments will be censored at the date of the last assessment prior to those missed assessments. For subjects with only one missed assessment, the documented progressive disease status and assessment date will be used. Time to progression (TTP) will be determined in a similar fashion as PFS, with the only difference being TTP will be censored at the death date for subjects who die without progressive disease.

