13.3 Analysis Populations

For the Phase I part of the study, the dose escalation and MTD evaluation will be conducted on the population who initiate Cycle 1, Day 1 treatment, and who meet the DLT evaluable criteria as described in Section 4.3. For the Phase II part of the study, the PFS4 evaluable population will include all subjects who initiate treatment with ruxolitinib, have experienced a PFS event within 4 months from the start of ruxolitinib treatment, or have at least 4 months of follow up time from the start of ruxolitinib treatment. The primary efficacy analysis will be conducted on the PFS4 evaluable population. Response-evaluable population will include all subjects (both Phase I and Phase II) who have baseline evaluation, measurable disease, and initiate study

treatment followed by at least one efficacy measurement. All response endpoints will be conducted on the response-evaluable population.

All other efficacy and ruxolitinib safety analyses will be conducted on the population of subjects (both Phase I and Phase II) who initiate treatment with ruxolitinib. Additionally, an analysis will be conducted on safety data collected from Cycle 1 through the cycle prior to initiation of ruxolitinib treatment (for all Phase II subjects initiating Cycle 1 with carfilzomib plus dexamethasone).

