18.5 Table of Events

Evaluation	Days -21 to -1 (Baseline)	Phase I and Phase II All Cycles ^t (cycle = 28 days) Subjects in Phase II/Run-In period only: Please note cycle numbers will start over with 'Cycle 1' after initiation of ruxolitinib							End of Treatment ^q	Follow-up ^r
		Day 1	Day 2 ^x	Day 8 ^x	Day 9 ^x	Day 15 ^x	Day 16 ^x	Day 22 ^x		
Informed consent ^a	X									
Inclusion/exclusion	X									
Medical and disease history ^b	X									
Physical examination/BSA ^c	X	X ^s							X	
Vital signs ^d	X	X	X	X	X	X	X	X	X	
ECOG performance status	X	X ^s							X	
Pregnancy test ^e	X								X	
Electrocardiogram	X									
Echocardiogram, MUGA, or cardiac MRI ^f	X	X (prior to every 2 cycles)							X	
Hematology ^g	X	X ^s	X	X	X	X	X	X	X	
Coagulation ^h	X	X ^s								
Blood chemistries ⁱ	X	X ^s		X		X		X	X	
BNP ^w		X ^s								
Viral hepatitis panel ^v	X									
HBV DNA testing ^y	X									
Bone marrow ^j	X	(X)							X ^l	(X) ^r
Correlative studies (Blood and bone marrow) ^l	X			X ^l (Cycle 1 of ruxolitinib only; Blood only)				X ^l (Cycle 1 of ruxolitinib only day 20 -27)	X ^l	
Response assessments (SPEP/UPEP, IFE, SFLC) ^{k,u}	X	X							X	(X) ^r
Serum β2-microglobulin	X									
Assessment of plasmacytoma ^m	X	(X)							(X)	(X) ^r
Bone skeletal survey ⁿ	X	(X)							(X)	
Carfilzomib administration ^o		X	X	X	X	X	X			

Ruxolitinib administration ^o		Twice Daily days 1 – 28 Phase I all subjects. Phase II: Subjects with < PR following Phase II/Run-In period, subjects ≥ PR following Phase II/Run-In period who then subsequently progress, and subjects who proceed directly to Phase II/Ruxolitinib							
Dexamethasone administration ^o		X		X		X			
Concomitant medications ^p	X	=====→						X	
Adverse event monitoring		=====→						X	
Follow-up									X ^r

(X) only if clinically indicated

- a) All subjects must sign an IRB-approved informed consent document prior to enrollment and prior to any study related procedures.

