- g) Hematology: hemoglobin, WBC with differential, and platelet count.
- h) Coagulation: prothrombin time (PT), international normalized ratio (INR).
- i) Blood chemistry: sodium, chloride, potassium, magnesium, phosphate, uric acid, BUN, glucose (fasting at baseline), ALT/AST (SGPT/SGOT), alkaline phosphatase, total protein, total bilirubin, albumin, serum creatinine, and estimated creatinine clearance by Cockcroft-Gault Equations (Appendix 18.4) calcium and lactate dehydrogenase (LDH). Creatinine clearance required on days of the cycle other than Day 1 may be calculated using the Day 1 weight of the current cycle.
- j) Bone marrow aspirate to be collected at screening for % plasma cells, morphology, standard karyotype, cytogenetics by FISH and biomarkers. Repeat for % plasma cells at the time of CR and/or progression. Screening timepoint only: If bone marrow previously collected for pathology evaluation as previously described within 21 days prior to initiation of study therapy, the pathology evaluation does not need to be repeated as part of the screening assessments. However, a bone marrow aspirate must be performed for correlative studies (see Footnote L for information on correlative studies).

- k) Serum or urine protein electrophoresis (SPEP, UPEP), serum and urine immunofixation (IFE) and serum free light chain (SFLC) assay. To be conducted prior to each cycle (within 7 days of Day 1) until documentation of initial disease progression. For cycles delayed ≤ 7 days, repeat evaluations are not required. If the start of a new cycle is delayed > 7 days a repeat disease evaluation must be performed prior to the subsequent cycle. Phase II/Run-In subjects who cross over to Phase II/Ruxolitinib only: Disease responses will be calculated from disease evaluation performed just prior to initiating ruxolitinib (a new baseline will be established).

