- q) End of Treatment visit should be completed within 30 days of last dose of study drug with evaluation of safety at 30 days or prior to initiation of subsequent therapy (whichever comes first)
- r) Subjects who received ruxolitinib on study and discontinue therapy for reasons other than disease progression should continue to have disease assessments per standard of care done until progression or start of subsequent therapy. At such time, follow-up for overall survival status will take place every three months ± 7 days until death, lost to follow-up, or until the criteria defined for the final analysis (Section 13.4.1) are reached. Follow-up beyond the safety follow-up period is only required for subjects who received ruxolitinib. Follow-up may be completed by phone contact. Death information from public sources, e.g. death registry, obituary listing, etc. can also be used when it is available and verifiable
- s) C1D1 procedures do not need to be repeated if the screening procedure occurred within 5 days (this applies to C1D1 following screening; does not apply to C1D1 of Phase II/Ruxolitinib in subjects who cross over from Phase II/Run-In); Day 1 procedures for subsequent cycles do not need to be repeated if done within 3 days of Day 1.
- t) ± 3 day window permitted for holidays/administrative reasons
- u) Phase II/Run-In period only: Beginning with Cycle 1, disease evaluation results to assess response should be available for investigator review prior to dosing on Day 1 of each cycle (within 7 days of Day 1) until initiation of ruxolitinib (after ruxolitinib has been initiated, disease evaluation assessments will continue to be collected prior to dosing on Day 1, but results will not be required to be available prior to Day 1 dosing). Cycle numbers start over with the initiation of ruxolitinib and a new disease response baseline will be established.
- v) Viral hepatitis panel including HBsAg, HB core antibody, HB surface antibody, Hep C antibody and HIV at baseline only.
- w) BNP to be done Day 1 (± 3 days) of every cycle.

- x) A +/- 1 day window is allowed for study treatment on Days 2, 8, 9, 15, and 16 and procedures on Day 22, unless otherwise noted. All procedures required for Days 2, 8, 9, 15, and 16 should be performed within 1 day of study treatment, unless otherwise noted.

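### After study therapy stops without progression, the plan fixes no disease-assessment interval up to month 4 and has no PFS4 rule for a missing or late assessment, so unseen progression can count as success

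*Combined protocol and SAP*

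**What the plan says.** **On treatment.** Footnote k of the Table of Events (18.5) ties serum and urine electrophoresis, immunofixation and free light chains to cycles: "To be conducted prior to each cycle (within 7 days of Day 1) until documentation of initial disease progression".

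**After stopping without progression.** Three places leave assessments to local practice and give no interval:
- Section 8.4.1: "response assessment samples should also be collected per standard of care during the follow-up visits".
- Section 8.6: "should continue to have standard of care disease assessments done until progression or start of subsequent therapy".
- Footnote r of 18.5: "should continue to have disease assessments per standard of care done until progression or start of subsequent therapy".

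The follow-up column of 18.5 shows response assessments with the bracketed mark used for tests done when clinically indicated, and refers to footnote r. One assessment is fixed: the same laboratory tests at the End of Treatment visit. Under 8.5 that visit replaces a scheduled visit if the decision to stop is made there. Otherwise it falls within 30 days of the last administration or before new therapy, whichever is earlier.

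**Endpoint.** Section 13.2.2 defines PFS4 as a yes/no variable, alive and progression free at 4 months from the start of ruxolitinib. Section 13.3 makes subjects evaluable if they have an event within 4 months "or have at least 4 months of follow up time from the start of ruxolitinib treatment". Section 13.4.1 uses the same trigger for both stages. Section 13.2.3 dates progression to the assessment that found it and, for survivors without documented progression, says "PFS will be censored at the date of last disease assessment". That section covers time-to-event PFS. Neither 13.2.2 nor 13.4.2.1 carries its censoring over to PFS4.

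**The concern.** IMWG progression (18.3) is largely a laboratory finding, so it is recorded when someone tests for it. Suppose a subject stops for toxicity in month 2, has a clean End of Treatment assessment, progresses in month 3 and is next tested in month 5. Progression is then dated to month 5. At month 4 the subject is alive, has no recorded event and has 4 months of follow-up, so 13.2.2 and 13.3 together allow a PFS4 success. Had there been no later test at all, 13.2.3 would censor the same subject at the End of Treatment assessment for PFS, while the binary endpoint could still count a success.

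Under that scoring the error runs in one direction. The trial is single-arm against a fixed 25%, so no control group shares the error, and the design has less than one percentage point of slack below its nominal alpha of 0.10. The same count drives the stage 1 decision.

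**Working it through.** **Inputs (13.1.2).** Null PFS4 rate 0.25 (2-month median: 0.5^(4/2)); alternative 0.50 (4-month median: 0.5^(4/4)); continue with at least 3 of 10; reject with at least 11 of 30; one-sided alpha 0.10; power at least 90%.

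**The plan's own figures.** For a success probability p,

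P(reject) = Σ over x = 3,…,10 of Bin(x; 10, p) × P[Bin(20, p) ≥ 11 − x].

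This gives 0.0914 at p = 0.25 and 0.9116 at p = 0.50. The stated alpha and power reproduce. Both figures assume that every progression before month 4 is captured.

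**Effect of unseen progression.** Let m be the share of all subjects whose progression before month 4 is not seen by then and is scored as success. Under the null the apparent rate is 0.25 + m.

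| m (assumed) | Apparent rate | P(continue after stage 1) | P(reject) |
|---|---|---|---|
| 0 | 0.250 | 0.474 | 0.091 |
| 1% | 0.260 | 0.504 | 0.114 |
| 2.5% | 0.275 | 0.548 | 0.155 |
| 5% | 0.300 | 0.617 | 0.237 |

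One subject in 30 is 3.3 percentage points.

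**What m might be.** m = (share stopping event-free before month 4) × (share of those whose progression is missed). Under the null's 2-month median, a subject event-free at month 2 progresses by month 4 with probability 1 − 0.5^(2/2) = 0.50. So m = 2.5% corresponds to 5% stopping at month 2 with every later progression missed, and m = 5% to 10% stopping. That is near worst case. If the End of Treatment assessment falls at month 3, the missable share is 1 − 0.5^(1/2) = 0.293:
- 5% stopping: m = 0.05 × 0.293 = 1.5%, P(reject) = 0.126.
- 10% stopping: m = 0.10 × 0.293 = 2.9%, P(reject) = 0.167.

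**Isolating the loss of the schedule.** A simulation of 1,000,000 subjects used exponential PFS with a 2-month median, took all events to be progressions, and set a 20% chance of stopping for other reasons over 4 months, so that about 11% stop before progressing. Off-treatment intervals were counted from the stop.

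| Off-treatment assessments | Observed PFS4 | P(reject) |
|---|---|---|
| Every 28 days | 0.282 | 0.176 |
| Every 2 months | 0.297 | 0.224 |
| Every 3 months | 0.305 | 0.256 |
| None | 0.335 | 0.375 |

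The first row exceeds 0.091 mainly because the last 28-day visit before month 4 falls about day 112. That alone gives 0.279 and 0.167 with nobody stopping, and it is a separate matter. The effect of losing the schedule is the rise over the first row: 0.048 at 2-monthly and 0.080 at 3-monthly testing.

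**The case against.** The strongest reply is that no sentence scores an unassessed subject as a success. A reader might infer such a rule from 13.2.2 and 13.3, but the text says only alive and progression free, and follow-up time is not defined. It could be read as time under disease assessment, in line with the censoring in 13.2.3. On that reading the subject is not evaluable and enrolment continues until the evaluable number is reached (4.3). This stands: the plan leaves the classification open. It is still a gap in the primary endpoint, and the other reading is equally available.

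Three further inferences go beyond the documents:
- *That testing becomes less frequent.* Standard of care might be monthly. What is lost is a fixed schedule; a lower frequency is not shown.
- *That a telephone call can establish freedom from progression.* Footnote r does say "Follow-up may be completed by phone contact", but after describing the three-monthly survival follow-up, which is its natural subject. The same footnote expects disease assessments to continue.
- *That stopping ruxolitinib alone triggers the change.* The trigger in 8.4.1 and 8.6 is stopping study treatment.

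The End of Treatment assessment also narrows the gap, as the smaller figures above show, but for an early stopper it can fall well before month 4. Finally, the synopsis plans a Kaplan-Meier 4-month rate and 13.4.2.2 plans landmark rates. With the censoring of 13.2.3 these would censor subjects who have no later assessment, and so could expose a discrepancy. They do not replace the binomial test in 13.4.2.1 that decides the trial.

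**Conclusion.** The concern holds as a gap in the plan, and the sponsor should fix it. For subjects who stop study therapy without progression before month 4, the documents neither secure a disease assessment near the landmark nor say how to score its absence. Progression before month 4 that is first tested later can therefore enter the primary count as a success.

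The design has little room for this: a 1% unseen share takes type I error from 0.091 to 0.114, above the nominal 0.10, and 2.5% or 5% gives 0.155 or 0.237. These figures rest on assumed shares and on scoring such subjects as successes. The documents give no early-stopping rate and no standard-of-care interval, so the actual size is unknown. With monthly testing after the stop, the added effect would be close to nil.

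**What to change.** **Assessments (8.4.1, 8.6, footnotes k and r).** Keep the 28-day laboratory disease assessments, counted from the start of ruxolitinib, whatever the treatment status, until progression, new anti-cancer therapy or the assessment that covers the 4-month landmark.

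**Endpoint and population (13.2.2, 13.3).** Define follow-up time by disease assessment. A PFS4 success needs no progression dated on or before 4 months and a progression-free assessment in a pre-specified window around the landmark. Subjects without such an assessment, including those who start new therapy first, stay in the denominator as not progression-free. Report the alternative scoring and the synopsis's Kaplan-Meier 4-month rate as sensitivity analyses, and reconcile the synopsis with 13.4.2.1.

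**Window.** It must include the scheduled pre-Cycle 5 assessment (about days 105–112). Requiring a clean test at or after 4 months would defer the decision to the pre-Cycle 6 test (about days 133–140) and turn subjects whose progression is dated after 4 months into failures. Under the alternative's 4-month median and 30.44 days per month, the success rate would be 0.5^(133/121.75) = 0.469 to 0.5^(140/121.75) = 0.451, and power would fall from 0.912 to between 0.856 and 0.813.

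**Cost.** Amendment wording, a few extra routine laboratory tests in early stoppers, and possibly a slightly lower PFS4 figure. N = 30 and the 3/10 and 11/30 rules do not change. The change must be prospective, because a test not done by month 4 cannot be recovered.

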8.7 Off-Study

Subjects will remain on study until the criteria for the final analysis have been met. Reasons a subject may be removed from the study early include, but are not limited to:

- Subject non-compliance with study participation, in the opinion of the investigator
- The subject or legal representative (such as a parent or legal guardian) withdraws study consent
- The subject is lost to follow-up
- Investigator's decision to withdraw the subject
- Subject death
- Early study termination

Subjects who do not receive ruxolitinib will be taken off study after completion of the safety monitoring period (Section 9.3)

When subjects are removed from the study, the reason for study removal and date the subject was removed should be documented.

Subjects that are Off Study will not participate in any study related procedures, including data collection. The study will be considered complete when one or more of the following conditions is met:

- All subjects have completed all study visits.

- All subjects have discontinued from the study.
- The IRB, LCI DSMC, Sponsor-Investigator or Amgen or Incyte discontinues the study because of safety considerations.
- The Sponsor-Investigator defines an administrative or clinical cut-off date.

8.7.1 Subject Withdrawal

In all cases, the reason for withdrawal must be recorded in the subject's medical record and/or research chart and CTMS.

8.7.2 Screen Failures

A subject who, for any reason (e.g. failure to satisfy the selection criteria or withdraws consent), terminates the study before receiving first dose of the study regimen (Cycle 1, Day 1) is regarded as a "screen failure".

9 ADVERSE EVENTS

9.1 Adverse Event

An adverse event (AE) is any symptom, sign, illness or experience that develops or worsens in severity during the course of the study. Intercurrent illnesses or injuries should be regarded as AEs. Abnormal results of diagnostic procedures are considered to be AEs if the abnormality:

- results in study withdrawal
- is associated with a serious AE
- is associated with clinical signs or symptoms
- leads to additional treatment or to further diagnostic tests
- is considered by the Investigator to be of clinical significance

9.2 Serious Adverse Event (SAE):

An event is "serious" if it involves considerable detriment or harm to one or more persons (who may or may not be participants) or required intervention to prevent one or more persons from experiencing considerable detriment or harm. SAEs include:

- Death
- Life-threatening experience – Disease or condition where the likelihood of death is high unless the course of the disease/condition is interrupted or diseases/conditions with potentially fatal outcomes where the end point of the clinical trial analysis is survival
- Inpatient hospitalization or prolongation of hospitalization
- Persistent or significant disability/incapacity

- Congenital anomaly/birth defect in subject's offspring
- Any other important medical event that, based upon appropriate medical judgment, may jeopardize the participant, and may require medical or surgical intervention to prevent one of the outcomes listed above. Examples include allergic bronchospasm requiring intensive treatment in an emergency room or at home, blood dyscrasias or convulsions that do not result in inpatient hospitalization, the development of drug dependency or drug abuse, suicidal ideation or attempts, or the unintentional revealing of some genetic information to insurers.

9.2.1 Related:

An event is "related" if, in the opinion of the Investigator, it was definitely or possibly was caused by the research activity.

9.2.2 Unexpected:

An event is "unexpected" when its specificity, nature, severity or incidence is not accurately reflected in the investigator's brochure or Package Insert previously reviewed and approved by the IRB. Examples include a lower rate of response to treatment or a side effect that is more severe than initially expected.

